##### **Not treatment emergent AE(s) summary:**

- Listing of (not treatment emergent) AEs showing treatment group, subject identifier, SOC, PT, verbatim term, date and day of onset, end date/time, duration, outcome, severity, date of death (if relevant), relationship to study treatment, action taken, AE seriousness and criteria.

##### **TEAE(s) summaries:**

The following TEAE summaries will be generated for the Safety Population.

Overview of TEAEs, summarizing number (%) of subjects with any

- (related/all) TEAE
- (related/all) Serious TEAE
- (related/all) TEAE leading to death
- (related/all) TEAE of grade 3 or higher
- (related/all) TEAE leading to drug interruption
- (related/all) TEAE leading to study discontinuation
- (related/all) TEAE of special interest (AESI)
- (related/all) TEAE leading to permanent discontinuation

- TEAEs by primary SOC and PT, showing number (%) of subjects with at least one TEAE, sorted alphabetically by SOC and decreasing incidence of PTs within SOC for the ublituximab arm. This sorting order will be applied to all other tables, unless otherwise specified.
- TEAEs by PT, sorted by decreasing frequency in the ublituximab arm
- Common TEAEs (incidence  $\geq 2\%$  in any treatment group for PT) by primary SOC and PT, showing number (%) of subjects with at least one common TEAE.
- All at least possibly drug related (to IV and/or oral study treatment) TEAEs by primary SOC and PT, showing number (%) of subjects with at least one possibly related TEAE, sorted by sorting order defined above.
- All TEAEs by maximal severity, presented by primary SOC and PT, showing number (%) of subjects with at least one TEAE by severity (ie, mild, moderate, or severe), sorted by sorting order defined above.
- Listing of TEAEs showing treatment group, subject identifier, SOC, PT, verbatim term, date and day of onset, end date/time, duration, outcome, severity, date of death (if relevant), relationship to study treatment, action taken, AE seriousness and criteria.

#### **AESI summaries:**

- Treatment-emergent AESI by primary SOC and PT, showing number (%) of subjects with at least one TEAE, sorted alphabetically by SOC and decreasing incidence of PTs within SOC for the Ublituximab arm. This sorting order will be applied to all other tables, unless otherwise specified.
- Listing of treatment-emergent AESI showing treatment group, subject identifier, SOC, PT, verbatim term, date and day of onset, end date/time, duration, outcome, severity, date of death (if relevant), relationship to study treatment, action taken, AE seriousness and criteria.

#### **Treatment-Emergent Suicidal Ideation and Behavior (SIB)**

- Treatment-emergent SIB events will be summarized by treatment group, showing number (%) of subjects with at least one TEAE of suicidal ideation and behavior, and number (%) of subjects for each PT.
- A listing of suicidal ideations and behaviors will also be presented.
- Additional SIB analyses may be conducted as needed, such as follow-up time adjusted incidence rates of SIB event.

#### **Serious TEAE(s) summaries:**

- All serious TEAEs by primary SOC and PT, showing number (%) of subjects with at least one serious TEAE, sorted by sorting order defined above.
- All at least possibly related (to IV and/or oral study treatment) serious TEAEs by primary SOC and PT, showing number (%) of subjects with at least one possibly related serious TEAE, sorted by sorting order defined above.
- All serious TEAEs by seriousness criteria, presented by primary SOC and PT, showing number (%) of subjects with at least one serious TEAE by seriousness criteria.

- Listings of SAEs showing treatment group, subject identifier, SOC, PT, verbatim term, date and day of onset, end date/time, duration, outcome, severity, date of death (if relevant), relationship to study treatment, action taken, AE seriousness and criteria.

### **TEAE(s) leading to treatment discontinuation summaries:**

These events will be selected by the eCRF variables “Action taken with IV study treatment” and/or “Action taken with Oral study treatment” = “Permanently discontinued”.

- All TEAEs leading to treatment discontinuation, by primary SOC and PT, showing number (%) of subjects with at least one TEAE sorted by sorting order defined above.
- 
- Listings of TEAEs leading to treatment discontinuation showing treatment group, subject identifier, SOC, PT, verbatim term, date and day of onset, end date/time, duration, outcome, severity, date of death (if relevant), relationship to study treatment, action taken, AE seriousness and criteria.

### **Deaths summaries:**

- Number (%) of subjects who died during the study period will be shown by treatment group.
- Death in non-randomized subjects or randomized but not treated subjects will be listed.
- All TEAEs leading to death, by primary SOC and PT, showing number (%) of subjects sorted by sorting order defined above.
- Listings of deaths showing treatment group, subject identifier, gender, race, age, duration of exposure, date of death (if relevant), causes and circumstances surrounding the death

#### 2.4.5.2 Analysis of Laboratory Variables

Clinical laboratory variables that will be analyzed include hematology tests, serum chemistry tests, pancreatic enzymes, a coagulation test, and urinalysis (see Section 2.1.4.2 for the complete list of parameters).

Summary statistics (including mean, SD, median, Q1, Q3, minimum and maximum) of all laboratory variables (raw data and changes from baseline) will be calculated for each visit. Mean changes from baseline with the corresponding standard deviation will be plotted over time (at same time points) in each treatment group for selected parameters using box plots, which include hemoglobin, lymphocytes, neutrophils, platelets, ALT, AST, TBL, and serum creatinine (and CrCL).

Subjects with laboratory values outside of the normal reference range at any post-baseline assessment will be summarized and graded per NCI CTCAE Version 4.03 when applicable. Subject incidence of laboratory toxicity will be summarized by treatment group and maximum grade for each laboratory test. Shift tables between baseline and worst post-baseline results will also be presented.

A listing of subjects with at least one post-baseline abnormal lab test will be provided and will display the complete profile over time of all values of corresponding test. In this listing, baseline, endpoint value and individual values will be flagged when lower or higher than the lower or upper laboratory limits and/or when reaching the absolute limit of abnormality criteria.

## Drug-Induced Liver Injury (DILI)

The liver function tests, namely AST, ALT, total bilirubin (TBL), and alkaline phosphatase are used to assess possible drug induced liver injury. The proportion of subjects with abnormal values at any post-baseline visit by baseline status will be displayed by treatment group for each parameter. The proportion of subjects with abnormal values at any post baseline visit will also be displayed by duration of exposure for each treatment group.

Time to onset of the initial ALT and AST elevation ( $>3x$  ULN) and total Bilirubin elevation ( $>2x$  ULN) will be analyzed using Kaplan-Meier estimates, presented by treatment group. Evaluations of drug-induced serious hepatotoxicity (eDISH) plot (Hy's Law graphs) of distribution of peak values of ALT, AST and the maximum of ALT and AST versus peak values of total bilirubin will also be presented. Note that the ALT/AST and Total bilirubin values will be presented on a logarithmic scale. The eDISH plots will be divided into 4 quadrants with a vertical line corresponding to  $3x$  ULN for ALT and/or AST and a horizontal line corresponding to  $2x$  ULN for total bilirubin. Similarly, a graph for ALT vs. TBL and a graph for AST vs. TBL will be provided.

The normalization (to  $\leq 1$  ULN) of elevated liver function tests will be summarized by categories of elevation ( $\geq 3x$ ,  $\geq 5x$ ,  $\geq 8x$ ,  $\geq 10x$ ,  $\geq 20x$  ULN for ALT, AST, ALT or AST,  $\geq 1.5x$ ,  $\geq 2x$  ULN for alkaline phosphatase, and  $\geq 1.5x$ ,  $\geq 2x$  ULN for total bilirubin), with following categories of normalization: not normalized, normalized after temporary discontinuation of study medications, normalized after permanent discontinuation of study medications. Note that a subject will be counted only under the maximum elevation category.

### 2.4.5.3 Analyses of Vital Sign Variables

The summary statistics (including mean, SD, median, Q1, Q3, minimum and maximum) of all vital signs variables (raw data and changes from baseline) will be calculated for each visit by treatment group and presented. Mean changes from baseline with the corresponding standard deviations will be plotted over time (at same time points) in each treatment group.

The incidence of abnormal vital signs at any time during the observation period will be summarized by treatment group. A shift table from baseline to worst vital sign status during the observation period will be presented.

A listing of subjects with at least one post-baseline abnormal vital signs observation will be provided and will display the whole profile over time of all parameters.

### 2.4.5.4 Analysis of Physical Examination Variables

The incidence of abnormal findings per body system will be tabulated by visit and for the whole post-baseline observation period. Free text specifications will be listed.

### 2.4.5.5 Analysis of Electrocardiogram Variables

ECG interpretation will be tabulated as frequencies by visit and time point, and in a shift table of baseline vs. worst post-baseline observation. Results per time point and free-text specifications of abnormalities will be listed.

#### 2.4.6 Duration of Study Treatment Exposure and Compliance

The duration of study treatment exposure and compliance will be summarized by actual treatment within the safety population as continuous and categorical variables.

##### **Duration of oral study treatment exposure**

Duration of exposure (to oral study treatment/placebo) will be summarized descriptively as a quantitative variable (N, mean, SD, median, Q1, Q3, minimum, and maximum).

The cumulative duration of treatment exposure, defined as the sum of subjects' duration of treatment exposure in subject years, will be summarized by treatment group.

##### **Treatment compliance / Exposure to IV study treatment**

Treatment compliance for both ublituximab/IV placebo and teriflunomide/oral placebo will be summarized as quantitative variables (N, mean, SD, median, Q1, Q3, minimum, and maximum). The percentage of subjects who have a compliance of <80%, 80% to <100%, and  $\geq 100\%$  will be tabulated by treatment group.

Furthermore, for teriflunomide or oral placebo, the proportion of months on at least 80 percent of prescribed oral medication will be calculated with the following algorithm:

1. For every period between a dispensation of tablets and the succeeding dispensation (or the last return), the ratio #tablets taken/#duration or the period in days is calculated
2. This calculated ratio is assigned to each day of the containing period
3. For each full 28 day period starting on the first day of oral treatment (or the potentially shorter last period) the fractions are added and divided by the number of days in this period. This result is compared with the defined threshold (0.8 / 80%), and for each subject the percentage of periods reaching the threshold will be calculated and summarized.

#### 2.4.7 Analyses of Pharmacokinetics

##### **Pharmacokinetics for ublituximab**

Population PK (nonlinear mixed effect modeling) analyses will be performed by an independent vendor and reported separately. This analysis will assess dose- and time-dependent kinetics as well

as covariates effects on the PK of ublituximab.

Exposure-response relationships for efficacy and safety will be evaluated to determine the recommended therapeutic dose.

The population PK and exposure-response analyses will be conducted using the PK population that will consist of subjects who have at least one baseline and one post-baseline PK assessment. Subjects will be excluded from the PK analysis if data are incomplete which may influence the analysis. Excluded cases will be documented together with the reason for exclusion.

Pharmacokinetics data will be reported based on all subjects treated with ublituximab with any PK samples.

### **Plasma Concentration for teriflunomide**

In order to assess teriflunomide compliance, four plasma samples will be taken from all subjects. The first sample will be taken prior to oral administration of teriflunomide or oral placebo on Week 1 Day 1. The second sample will be taken prior to infusion of ublituximab or IV placebo on Week 48. The third sample will be taken at Week 96, prior to first dose of elimination therapy. The last plasma sample for teriflunomide will be taken at Week 116 and will be used to determine that teriflunomide has been eliminated from all subjects following the accelerated elimination procedure with either active charcoal or cholestyramine. For subjects who withdraw from treatment early, a blood sample will be collected at the Early Withdrawal from Treatment visit prior to first dose of elimination therapy.

Only plasma samples from subjects treated with teriflunomide will be analyzed for plasma teriflunomide concentrations. See the Laboratory Manual for PK collection and processing instructions.

The plasma concentration of teriflunomide for each subject will be presented for each time point in a data listing. Descriptive statistics will be used to describe the plasma concentration for each timepoint. A timeplot of the average plasma concentration over time will be constructed.

#### **2.4.8 Analyses of Anti-Drug Antibody (ADA)**

Immunogenicity to determine the absence or presence of ADA will be done for only the subjects randomized to ublituximab. Immunogenicity results, specifically the impact of ADA on the PK of ublituximab, will be reported in conjunction with the population PK analysis. . The percentage of

subjects developing ADA will be summarized by actual treatment group. A listing will be provided for ADA data.

### 2.4.9 Analysis of Pharmacodynamics

B lymphocyte cell counts (% CD19+ B cells) will be tabulated per scheduled time point together with absolute and percentage changes from baseline.

## 2.5 Data Handling Conventions

Data handling discussions for the primary efficacy is included in Section 1.2.1. The further discussion for the data handling conventions for other variables will be included in this section.

### General conventions

The following formulas will be used for computations of parameters.

Demographic formulas:

The age variable recorded in the eCRF will be used for analysis, no derived age variable is planned as only the year of birth is reported.

$$\text{BMI (in kg/m}^2\text{)} = \frac{\text{weight in kg}}{\text{height (in cm)} \times \text{height (in cm)}} \times 10000$$

Renal function formulas:

Creatinine clearance value will be derived using the equation of Cockcroft and Gault. The calculation requires body weight and age. The last weight measurement on or before the visit of the creatinine measurement will be used. If available, the age used by central lab at the visit will also be used for this derivation, otherwise the age at informed consent will be used.

$$\text{crcl (mL/ min)} = \frac{(140 - \text{age}) \times \text{weight(kg)}}{0.814 \times \text{creatinine(umol / L)}} \quad (\text{For males})$$

$$\text{crcl (mL/ min)} = \frac{(140 - \text{age}) \times \text{weight(kg)}}{0.814 \times \text{creatinine(umol / L)}} \times 0.85 \quad (\text{For females})$$

### 2.5.1 Missing Data

For categorical variables, subjects with missing data are not included in calculations of percentages unless otherwise specified. The number of subjects with missing data will be presented.

For data listings, the character date will always be used to present the date collected in the eCRF, which allows the actual recorded date to be shown if elements are unknown/missing.

#### 2.5.1.1 Multiple sclerosis medical history variables

If the date of first MS diagnosis, first symptoms of MS, most recent relapse onset or start and end of previous MS treatments are incomplete, (i.e., month is unknown or day is unknown), unknown month/day will be set to July 1st, an unknown day will be set to the 15th.

#### 2.5.1.2 Date of first and last treatment intake

For all treated subjects, first treatment date is the date recorded on the baseline CRF.

If first dose day is missing and first dose month and year are not missing:

Impute first dose date using the first day of the month. If this leads to a date before first drug dispense date, use the first drug dispense date instead. Imputation flag is 'D'.

If first dose month is missing and first dose year is not missing:

Impute first dose date using 1 January as the day and month. If this leads to a date before first drug dispense date, use the first drug dispense date instead. Imputation flag is 'M'.

If first dose year is missing:

Impute first dose date using the first drug dispensing date if the subject did not return all medication. Imputation flag is 'Y';

Last treatment intake date is collected on eCRF page. For treated subjects, if the date is incomplete,

If last dose day is missing, and last dose month and year are not missing:

Impute last dose date using the last day of the month. If this leads to a date after study completion/discontinuation date, use study completion/discontinuation date instead. Imputation flag is 'D'.

If last dose month is missing, and last dose year is not missing:

Impute last dose date using 31 December as the day and month. If this leads to a date after study completion/discontinuation date, use study completion/discontinuation date instead. Imputation flag is 'M'

If last dose year is missing:

Impute last dose date using study completion/discontinuation date. Imputation flag is 'Y'.

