 - Compliance will also be assessed by inspection of the blister packs and counting of the used and unused tablets at each visit by the study site. Details of teriflunomide or oral placebo (date and time of first dose, last dose prior to visit, number of tablets dispensed and number of returned tablets) will be recorded in the eCRF.

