#### 2.1.3.1 Primary Efficacy Variable

The primary efficacy variable (per patient) is the number of IRAP-confirmed relapses (recorded in the eCRF as “Was the relapse adjudicated as protocol defined relapse by IRAP?”=Yes) which started (Start Date of Suspected Relapse Symptoms) on or after the day of randomization and up to the day of last study treatment. If the exact start date of relapse symptoms is unknown, the relapse will be assumed to have started during this period unless sufficient information is available to conclude that the symptoms started before or after (e.g. in case of missing start day, the symptoms start month is after the month of treatment end).

Annualized Relapse Rate will be summarized within treatment group as the ratio of the sum of all patients’ relapse counts divided by the sum of all patients’ treatment duration (in years). Years under treatment will be derived as:

Treatment years =  $(\text{date of last treatment intake (oral or IV)} - \text{date of randomization} + 1) / 365.25$ .

The statistical testing approach is described in section 2.4.3.1.

Please see below for the assessment process of suspected relapses.

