## 2.4.2 Primary Efficacy Variable

### **Main statistical model and adjustment for covariates**

The primary analysis will be performed using the mITT with a Negative Binomial regression model to accommodate the potential over-dispersed data appropriately. The model will include the total number of confirmed relapses with onset between randomization date and the day of last treatment as response variable, treatment group, EDSS strata (baseline EDSS score  $\leq 3.5$  versus  $> 3.5$ ) and clinic region (defined in section 2.1.1) as covariates. There will be two treatment groups (teriflunomide or ublituximab). In order to account for different treatment durations among subjects, the log-transformed standardized treatment duration will be included in the model as an “offset” variable for appropriate computation of the annualized relapse rate. [REDACTED] will be used to assess the overall model with subjects in a repeated statement using a Generalized estimating equation (GEE) approach. The standardized treatment duration is defined as (date of last treatment – randomization date +1)/365.25.

Two-sided 95% confidence intervals of the rate ratio will be provided for the comparisons of ublituximab versus teriflunomide. The estimated relapse rate for each treatment group and the difference between them, together with the corresponding 2-sided 95% confidence intervals will be provided.

[REDACTED]

The “overall” estimated annualized relapse rates (number of relapses divided by the sum of years under treatment) will also be presented by treatment group.

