### **Handling of dropouts**

Dropouts are handled by using the offset variable in the model which adjusts for the duration of time on treatment. This is different than multiple imputation, which seeks to estimate the information that would be available after dropping out. The primary analysis includes confirmed relapses with onset from randomization to date of last treatment. Subjects who withdraw from study drug treatment can still be followed and participate in study visits. However, the primary analysis will only include the time from randomization until the date of last treatment.

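### The rule for an incomplete last-dose date is not capped at treatment end, so off-drug time can enter the primary on-treatment relapse rate

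*SAP*

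**What the plan says.** The date of last treatment does two jobs in the primary analysis. It closes the relapse count, which takes confirmed relapses starting "on or after the day of randomization and up to the day of last study treatment" (SAP 2.1.3.1). It also sets the offset: "The standardized treatment duration is defined as (date of last treatment – randomization date +1)/365.25" (SAP 2.4.2). The paragraph on dropouts in SAP 2.4.2 states the intent: "the primary analysis will only include the time from randomization until the date of last treatment".

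SAP 2.5.1.2 begins with "Last treatment intake date is collected on eCRF page" and then deals with incomplete entries in three steps:

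- Day missing: the last day of the known month.
- Month missing, year known: "Impute last dose date using 31 December as the day and month".
- Year missing: "Impute last dose date using study completion/discontinuation date".

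The first two steps share one limit: "If this leads to a date after study completion/discontinuation date, use study completion/discontinuation date instead". Neither document defines that study date. The last-dose rule uses no drug record. The first-dose rule in the same section does, because it is bounded by the date of first dispensing.

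**The concern.** Leaving the study and stopping treatment are different events in this plan. SAP 2.3 tabulates subjects who stop drug but allow further assessments separately from those who end follow-up. SAP 2.4.2 says that subjects who stop drug may continue study visits. Relapses after drug withdrawal are meant for sensitivity analysis 3, which uses time on study as its offset.

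An imputation rule that runs to the study date puts off-drug days into an analysis defined as on-treatment, for any affected subject whose true last dose was earlier. A confirmed relapse in the gap is then counted as on-treatment. SAP 2.1.3.1 can add to this, because a relapse with an unknown start date is placed inside the treatment window unless there is enough information to exclude it.

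The same date also feeds the treatment-emergent window (30 days after last dose, SAP 2.4.5.1), the censoring of time to first relapse (SAP 2.4.4.10) and the duration of oral exposure (SAP 2.1.2).

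**Working it through.** The plan gives no figure for the effect of this rule, so there is none to reproduce. The check has two parts.

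**1. How far the date can move for one subject**

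Inputs: oral dosing ends on the last day of Week 95 (Protocol 4.3), which is 95 × 7 = Day 665. Week 96 is Day 672 and Week 116 is Day 812 (Protocol Table 7).

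- Completer, study completion read as Week 96: 672 − 665 = 7 days.
- Completer, study completion read as Week 116: 812 − 665 = 147 days, and 147/665 = 22% more exposure.
- Early stopper, taking Day 168 as an illustration, followed for the 20 weeks after last dose in Protocol 3.3: 20 × 7 = 140 days, and (168 + 140)/168 = 1.8 times true exposure.
- 31 December rule: at most 364 days, and only for someone who stayed in the study that long off drug.

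**2. What this does to an arm**

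Inputs: rates of 0.25 and 0.15 (worked example, SAP 1.3.1), giving a rate ratio of 0.15/0.25 = 0.600; mean follow-up of 1.75 years (SAP Table 1); 220 per group (SAP 1.3), so 220 × 1.75 = 385 person-years per arm. Two inputs are assumptions, because the documents give neither: the share *m* of subjects with an affected date, taken as equal in both arms, and the relapse rate after stopping drug.

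Arm rate = (on-drug rate × 1.75 + *m* × gap × off-drug rate) / (1.75 + *m* × gap), with the gap in years.

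For a gap of 147/365.25 = 0.4025 years and *m* = 5%, *m* × gap = 0.0201:

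- No relapses in the gap: 0.4375/1.7701 = 0.247 and 0.2625/1.7701 = 0.148; ratio 0.600.
- Off-drug rate 0.5 in both arms: (0.4375 + 0.0101)/1.7701 = 0.253 and (0.2625 + 0.0101)/1.7701 = 0.154; ratio 0.609.
- Off-drug rate 0.5 on teriflunomide and 0.15 on ublituximab: 0.253 and 0.150; ratio 0.593.

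The added time is 220 × 0.05 × 0.4025 = 4.4 person-years on 385, or 1.15%.

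The table gives the range of the rate ratio over five pairs of off-drug rates (teriflunomide/ublituximab): 0/0, 0.25/0.15, 0.25/0.25, 0.5/0.15 and 0.5/0.5.

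| Gap (days) | Share affected | Rate ratio (from 0.600) |
|---|---|---|
| 7 | 10% | 0.599 to 0.601 |
| 147 | 2% | 0.597 to 0.604 |
| 147 | 5% | 0.593 to 0.609 |
| 147 | 10% | 0.587 to 0.618 |
| 364 | 10% | 0.569 to 0.641 |

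The 147-day rows also serve roughly for early stoppers followed for 20 weeks (140 days). These are ratios of crude rates, not the fitted negative binomial model.

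**The case against.** The strongest reply is that the rule will seldom fire. It applies only to incomplete dates, and the eCRF must hold the date and time of each administration (Protocol 7.5) and the "last dose prior to visit, number of tablets dispensed and number of returned tablets" (Protocol 7.5.1.1). That stands as a limit on size. It also means that the data for a better bound are already collected.

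A reader might infer that washout relapses enter the primary rate for completers generally. The documents do not establish this. Protocol 6.10 calls Week 96 the end of study visit, Table 7 keeps End of Study apart from the Follow-up Period, and SAP 2.5.1.3 uses a separate end of follow-up date. The Protocol synopsis points the other way by counting the 20-week follow-up as participation. On the Week 96 reading a completer gains 7 days, which the offset wording in Protocol 8.9.1 already allows.

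A reader might also infer that subjects lost to follow-up gain long unobserved time. The cap includes study discontinuation, so this would need a discontinuation date recorded after last contact, and nothing says that happens. Nor do the documents settle on gaps of 504 days (Day 168 to Week 96) or more. Continued visits off drug make 504 days possible, but Protocol 3.3 and 6.10 describe 20 weeks of follow-up after stopping.

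Finally, sensitivity analysis 3 does not depend on the last-dose date. That is true, but it answers a different question and leaves the primary estimate uncorrected. For a subject with a missing year, the primary analysis largely coincides with it, so comparing the two would not reveal the error. If discontinuation was meant as stopping treatment, the cap would work; however, the wording ties it to the study.

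**Conclusion.** The point holds as a gap in the definition of the primary offset and relapse window. Subjects who stopped drug and remained in the study can have off-drug time labelled as treated, whether study completion means Week 96 or Week 116. Completers are materially affected only on the Week 116 reading.

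The expected effect is small. With 5% affected in both arms and a 147-day gap, the rate ratio lies between about 0.593 and 0.609 against 0.600. This rests on assumed shares and off-drug relapse rates. The direction is not fixed: added time without relapses lowers both arm rates and leaves the ratio unchanged when shares are equal, while off-drug relapses can move the ratio either way. A claim of systematic bias towards either arm is not supported. The change is still worth making, because it concerns the primary endpoint and costs very little.

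**What to change.** Amend SAP 2.5.1.2 as follows:

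1. Keep the known parts of the date and impute the rest, but cap the result at the earliest of the Early Withdrawal from Treatment visit, the final drug-return date and, for completers, the Week 96 visit.
2. Do not let the imputed date fall before the last documented infusion or recorded oral dose. If the floor and the cap conflict, documented intake should prevail. The last dose recorded before a visit should serve only as the floor, since it may precede the true stop and using it as the imputed value would cut real exposure.
3. Define the study completion/discontinuation date, and reconcile the end of a completer's offset between SAP 2.4.2 (last treatment) and Protocol 8.9.1 (which also mentions completion of the Week 96 assessment).
4. Report the number of imputed last-dose dates by arm, using the existing D, M and Y flags.

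The cost is one SAP paragraph and one revised date derivation. No new data are needed.
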